6.2.3 Hepatic Injury

The reticuloendothelial system can sequester immature blood elements, theoretically resulting in hepatic injury. An acute elevation of the AST/ALT hepatic enzymes > 900 U/dL in the first 24 hours post – infusion will trigger the stopping rules. This level is corresponds to the CTCAE v4.0 Grade 4 adverse event. It is unlikely that "end vessel" microthrombosis would occur in the liver due to the dual blood supply of the liver and the lung is the first pass organ.

6.2.4 Renal Complications

DMSO induces hemolysis of contaminating red blood cells during the hUCB storage and may also induce in vivo hemolysis and ultimately pigment nephropathy (Smith, 1987). To minimize the effect of these, our hUCB product will be washed according to Standard Operating Procedures prior to infusion. Though unlikely, it is possible that some quantity of DMSO will remain which could cause toxicity. Renal function/events corresponding to the CTCAE v4.0 Grade 3 will trigger the stopping rules.

IRB NUMBER: HSC-MS-12-0876
UTHeath
The University of Texas
The University of Texas

6.2.5 Neurologic Complications

The subject's acute neurologic status will be monitored hourly until discharged. Hourly GCS, pupillary size/reactivity, motor/sensory evaluation of extremities, and any seizure activity will be recorded from time of infusion to discharge. *Grade 3 – 5 central nervous* system event as defined in the NCI CTCAE v4.0 occurring within 12 hours of cellular product infusion will trigger the stopping rules. Other changes temporally related to cellular product infusion (those events occurring within 12 hours of infusion) will be considered associated with the protocol and recorded as an adverse event.

6.3 Psychological & Functional Outcome Assessment Tests

The following tests will be performed at baseline and all follow-up visits for children who have the visual, motor, and language abilities needed to complete the assessment tasks, (note table in Appendix B).

6.3.1 Motor Functioning

The Gross Motor Fine Motor - 88 Scale (GMFM-88) is an 88-item standardized, observation-based assessment of children's gross and fine motor abilities. It was designed for motor assessment of children with cerebral palsy. Administration time is 45-60 minutes.

6.3.2 Quality of Life

The parent(s) proxy version of the Cerebral Palsy Quality of Life Questionnaire (CP QOL) is measure of health related quality of life for children ages 4 through 12 years. The 66-item questionnaire assesses QOL across seven domains (1) social well-being and acceptance; (2) feelings about functioning; (3) participation and physical health; (4) emotional well-being; (5) access to services; (6) pain and feeling about disability; and (7) parent(s) health. Completion time is approximately 30-45 minutes. The questionnaire may be completed by telephone at a time convenient for Parent(s) prior to the study visit.

6.3.3 Adaptive Behavior Functioning

The Vineland Adaptive Behavior Scales -2^{nd} Edition (VABS-2), is a parent(s)/caregiver report measure that provides information regarding a child's adaptive behavior/daily living skills. The VABS-2 is appropriate for children from birth through age 10 and produces standard scores in the following domains: Communication, Daily Living Skills, Socialization, and Motor Skills. The measure takes between 25 and 90 minutes to complete.

The Pediatric Evaluation of Disability Inventory is a parent-report measure of adaptive functioning that is designed specifically for children with functional impairments and is sensitive to small changes in adaptive skills at the low end of the functioning spectrum.

6.3.4 Visual-Spatial Processing

The Motor Free Visual Perception Test- 3rd Edition (MVPT-3) will be administered to obtain information regarding visual perceptual abilities among children ages 4-10 years old across 5 domains: (1) spatial relationship, (2) visual closure, (3) visual discrimination, (4) visual memory, and (5) figure ground. Standard scores are produced and administration time is approximately 25 minutes.

6.3.5 Learning/Memory

The Narrative Memory subtest from the NEPSY-II, a developmental psychological battery for children, will be administered to obtain information regarding memory and learning ability: The Narrative Memory subtest can be administered to participants ages 3-10 years old and produces a standard score that indicates memory for organized verbal material under free recall, cued recall, and recognition conditions. Administration time will take approximately 10 minutes.

6.3.6 Expressive and Receptive Vocabulary

The Peabody Picture Vocabulary Test – 4th Edition (PPVT-4) produces a standard score indicating subjects' receptive one word vocabulary and will be administered to children ages 2.6-10 years old. Responses can be indicated either verbally or pointing to a picture and so is appropriate for all participants, regardless of motor abilities. Administration time is approximately 15 minutes. The PPVT-4 score is often considered an appropriate indication of general cognitive functioning. The Expressive Vocabulary Test - 2nd Edition (EVT-2) will provide a standard score indicating subjects' expressive one word vocabulary. Responses are provided verbally and so the test is appropriate for all children (ages 2.6-10 years old), regardless of motor abilities. Administration time is approximately 15 minutes.

6.4 MRI Evaluation

6.4.1 CP Neuroimaging

CP is a clinical diagnosis inclusive of a heterogeneous group of patients with differing patterns of neurological subtype (spastic -quadriplegic –hemiplegic –diplegic; ataxic/hypotonic; dyskinetic), severity (GMFCS level), type of lesion(s), location of lesion(s), and functional status (ambulatory/non-ambulatory). Although the pathogenesis of CP is still poorly understood, advanced neuroimaging studies have led investigators to the identification of some cerebral abnormalities frequently observed in young children with a diagnosis of CP (Towsley *et al.*, 2011). Such cerebral anomalies include the following: (1) periventricular white matter damage, (2) diffuse gray matter damage, (3) cerebral vascular accident, and (4) malformation of cortical development. Due to heterogeneity in etiological bases of primary and secondary insults to the developing brain which manifest as different cerebral anomalies, new interdisciplinary studies of CP are needed to evaluate cerebral anomalies in relation to neurological subtype and identifiable lesion types (and locations). Such an interdisciplinary approach has high potential to identify quantitative measures of brain structure with

IRB NUMBER: HSC-MS-12-0876
UTHealth IRB APPROVAL DATE: 10/23/2017

prognostic value as they explain neurological subtype, severity, and functional status. Such information is vital for the development of interventional strategies and predicting response to different types of interventions given the "profile" of each individual patient. Some neuroimaging studies have reported specific regions which are highly susceptible to being compromised in CP (Hoon et al., 2005; Hoon et al., 2009; Panigrahy et al.,2005; Son et al., 2007; Son et al.,2009; Thomas et al., 2005; Yoshida et al., 2010). By conducting an objective analysis which integrates quantitative measures of microstructural integrity (in white matter pathways) and quantitative measures of associated cortical/subcortical atrophy (in gray matter), the proposed study has the potential to identify neural systems compromised by CP and subsequently monitor response to treatment in a system-specific fashion.

Based on published literature (Towsley et al., 2011; Yoshida et al., 2011), spastic CP is expected to be predominately related to evidence of periventricular leukomalacia (PVL) or diffuse gray matter injury (GFCMS levels IV-V); or a cerebral vascular accident. In contrast, ataxic CP is expected to be related to white matter volume loss and increased mean diffusivity in deep gray matter structures (e.g. putamen, globus pallidum, and thalamus).

WM ROIs compromised in children with CP (Yoshida et al., 2011):

Anterior Limb of the Internal Capsule (ALIC) – dyskinetic = 1 FA Posterior Limb of the Internal Capsule (PLIC) – spastic & dyskinetic = \(\) FA External Capsule (EC)Posterior thalamic radiation – spastic & dyskinetic = \(\) FA

CC genu – dyskinetic = ↓ FA

CC splenium – spastic & dyskinetic = ↓ FA

CC_body – spastic = ↓ FA

Cingulum Bundle – dvskinetic = ⊥ FA

CST – spastic & dyskinetic = ↓ FA

SLF – spastic & dyskinetic = 1 FA

[figure not shown]
ILF – spastic & dyskinetic = ↓ FA

Thalamocortical pathways – spastic = 1 FA

GM ROIs compromised in children with CP:

Basal ganglia = ↓ volume Thalamus = ↓ volume Precentral Gyrus = ⊥ volume Postcentral Gyrus = ↓ volume Paracentral lobule = ↓ volume

6.4.2 MRI Acquisition and Analyses

The primary goal of acquiring whole brain MRI data is twofold: (1) to quantitatively assess macro- and micro-structural properties of GM and WM regions in two groups (+BMMNC / -BMMNC) using state-of-the-art neuroimaging acquisition/analysis methods and (2) to investigate macro- and micro-structural correlates of behavior in terms of cognitive performance and underlying neuropathology in a hypothesis – driven manner.

To accomplish these objectives, the MRI data needs to be collected using two different, yet complementary modalities of MRI: (1) high-resolution anatomical MRI (aMRI) and (2) diffusion tensor imaging (DTI). While data from both modalities is easily acquired in the same imaging session, the total scan time needs to be kept to the minimum necessary to achieve the specific aims within a timeframe generally well-tolerated by young children (e.g. ~30min). An earlier version of our proposed MRI protocol has been successfully completed by more than 400 children between the ages of 6 and 18 years old at our Imaging Research Facility during the course of ongoing NIH-supported studies involving diverse study populations including SBM, TBI, Learning Disabilities, and, typically-developing healthy controls. The following five pulse sequences constitute a complete imaging session: (1) conventional localizer/scout, (2) 3D isotropic T1-weighted MPRAGE, (3) 3D isotropic T2-weighted TSE, (4) 32-direction single-shot spin-echo diffusion sensitized echo-planar (DTI-32dir), and (5) 3D-FLAIR. Morphometric, diffusion tensor tractography, and DTI-derived metrics of microstructural properties of GM and WM (e.g. MD, FA) can all be performed in about 20 minutes. Parameters for each sequence are listed below in Figure 4.

Figure 4.

Sequence	Plane	Voxdim	Matrix	FoV	Flip (a)	TR (ms)	TE (ms)	TI (ms)	SENSE	Time
Scout	Sag	ē.					A 200 3		2	0'30"
3D T1-MPRAGE	Sag	1x1x1	256x256	256x256	8'	6.7	3.1	842	2	2'45"
3D T2-TSE	Sag	1x1x1	256x256	256x256	90°	2500	363		2	2'45"
3D FLAIR 32 dir DTI	Sag	2x2x2	256x256	256x256	50°	8000	330	2400	2	1'12"
(single shot EPI)	Ax b=1000	2x2x2	128x128	256x256	90°	7000	74		2	5'11"
Field map (Gradient echo)	Ax	2x2x2	128x128	256x256	90'	250	3.3		2	2'52"

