3. STUDY DESIGN

This is a randomized, blinded, placebo-controlled, cross-over study designed to treat CP in pediatric subjects with an IV infusion of autologous bone marrow mononuclear cells or autologous umbilical cord blood cells. A total of 30 subjects (15/arm) will be enrolled into the study. Subjects will be randomized 2:1 (treatment: sham). All subjects will return for follow-up at 6 months, 12 months, and 24 months post-treatment. At the 12 months post-treatment visit, those subjects who originally received the sham will be offered the BMMNC or hUCB treatment (Figure 1).

Figure 1.

Thirty subjects will provide a preliminary assessment of potential SAEs with a 10 to 15% incidence that we would be able to detect with reasonable confidence. The sample size would also allow us to acquire point estimates of different events that we would use for a larger efficacy study. The sample size determination is based on the historical treatment effect size of 15% decrease in gray and white matter volumes. Preservation

of this volume is based on the Phase 1 pediatric acute treatment of severe TBI using autologous bone marrow derived mononuclear cells as compared to historical control volumetric analyses by Wilde et al. (Wilde, E, et. al. 2005; Cox, C et al., 2011.)

Drug/Biologic: A single dose of intravenously administered autologous BMMNC or hUCB. The BMMNC dose will be 6X10⁶ cells/kg body weight infused over 15 minutes at a 1 million cells/ml concentration. For the hUCB arm, the minimum acceptable dose will be 2X10⁶cells/kg body weight based on rodent data (Lu, 2001), and the maximum allowable dose will be 10X10⁶cells/kg. The target dose will be the maximum available dose within this range. The bone marrow harvest, the hUCB reanimation, cell processing and product infusion will occur at Children's Memorial Hermann Hospital and the Griffin Stem Cell Laboratory.

Placebo: 0.9% saline will be infused in an identical syringe over the same rate as if receiving a cell infusion, (See "Blinding of Placebo Infusion").

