5.1.2 Randomization

The randomization sequence will be computer-generated. The subject will be assigned to the treatment or control arm in a 2:1 ratio using sequentially numbered, opaque, sealed envelopes prepared by a member of the Center for Surgical Trials and Evidence-based Practice (C-STEP) not involved in the clinical trial.

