6.4.9 Secondary Imaging Outcome Measures & Correlation with Functional Outcome

As noted in the section, "CP Neuroimaging", cerebral palsy is a clinical diagnosis comprising a heterogeneous group of patients. This heterogeneity is manifest both in the dominant clinical symptom complex, but also in the imaging correlates of the symptoms. To that end, prior to treatment this study will quantify the degree of functional impairment (GFCMS level), and correlate it with the CP subtype and imaging abnormality. The imaging ROIs will be prospectively identified pre-treatment. Then, according to the qualitative and quantitative metrics, the imaging data will be recorded. Post-treatment, these same ROIs will be compared to the baseline data, and correlated with any changes in functional outcomes as measured by specific tasks on the GFCMS. Ultimately, the changes in WM and GM ROIs that are associated with CP will be compared with and without treatment using autologous bone marrow derived mononuclear cells or autologous cord blood mononuclear cells. These data will provide a structural metric around which future studies could be powered. Further, these data may provide potential mechanistic targets in terms of structural preservation and restoration in patients with CP.

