9.1.2 Secondary Objectives/Outcomes

The models proposed will be tested using general linear models (GLM). We will examine all variables to determine that they are relatively symmetric and unimodal, examine group variances for obvious deviations, and examine the residuals from each model to ensure reasonable adherence to the assumptions of normality and independence. If any variables violate the assumptions, we might transform skewed variables. We will evaluate the comparability of our groups on key demographic variables and will covary variables if necessary (e.g., socioeconomic status). For Efficacy Outcome Measure 1 (refer to section 1.2.1), we will use repeated measures ANOVA or ANCOVA (including intracranial volume as a covariate for macrostructure analyses) with Group (Treatment, Control) as the between-subjects factor and Time of Assessment (baseline, 1 year, and 2 years) and Age as the within-subjects factors. We

will examine the Age x Group x Time interaction and two-way interactions for each analysis and will trim non-significant terms from each model. If GM and WM volumes or DTI metrics vary across time, we will complete trend analysis to identify whether a linear or quadratic function best fits the data. Dependent variables will be evaluated in separate analyses. Dependent variables will be 1) the volume of whole brain gray matter, white matter, and CSF; 2) FA of core white matter pathways (corpus callosum, arcuate/superior longitudinal fasciculus), and 3) MD of gray matter in frontal and temporal cortical regions.

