To examine brain-behavior relations (Efficacy Outcome Measure 2, section 1.2.2), we will first examine the distribution of variables to determine whether assumptions are met for Pearson or Spearman correlation approaches. To evaluate strength of brain-behavior relations, outcome scores will be correlated with specific macrostructural and microstructural metrics from the DTI. For global outcome, the GOS-EC score will be correlated with gray and white matter volumes and corpus callosum FA. For neurocognitive outcomes, the accompanying table shows the expected relations between outcomes and gray and white matter microstructural metrics. We expect positive correlation of dependent variables with FA and negative correlation of dependent variables with MD. Similar to our recent approach ([name] et al., 2012), brain-behavior analysis will also be completed using individual outcomes as dependent variables with group (Treatment, Control) and MRI/DTI variables as independent variables (e.g., examine the effect of group and FA of the corticospinal tract on fine motor scores; examine group and MD of dorsolateral frontal cortex on working memory scores).

Expected Relations of Neurocognitive Outcomes with Gray and White Matter						
Microstructure from Diffusion Tensor Imaging.						
Neurocognitive	Microstructure:	Microstructure:				
Outcome	Gray Matter MD	White Matter FA				
IQ		Corpus callosum				
Motor		Corticospinal				
GMFM-88						
Verbal Fluency		Arcuate/superior longitudinal				
PPVT4/EVT2		fasciculus				
Learning/Memory	Temporal cortex,					
NEPSY-II	hippocampus					

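### The +BMMNC / -BMMNC imaging label in section 6.4.2 contradicts the cells-versus-control comparison stated elsewhere, and the section 9.1.2 models have no term for the marrow or cord arm

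*Combined protocol and SAP*

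**What the plan says.** **Imaging groups.** Section 6.4.2 gives the purpose of the MRI data as assessing "macro- and micro-structural properties of GM and WM regions in two groups (+BMMNC / -BMMNC"). Section 6.4.9 says that the regions of interest will be "compared with and without treatment using autologous bone marrow derived mononuclear cells or autologous cord blood mononuclear cells". The secondary objective in 1.2 likewise sets autologous cells against the control group. Section 9.1.2 fits the repeated-measures imaging model "with Group (Treatment, Control) as the between-subjects factor", and the brain-behavior models "with group (Treatment, Control) and MRI/DTI variables as independent variables".

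**Arms.** Section 3 states: "A total of 30 subjects (15/arm) will be enrolled into the study". A child joins the marrow arm if no cord blood is banked (5.1.1) and the cord arm if it is banked with the named registry (5.2.3). A child whose unit proves unusable may be offered the marrow arm (5.2.5). Sections 5.1.2 and 5.2.5 each carry the same sentence, "The subject will be assigned to the treatment or control arm in a 2:1 ratio", at different points in the two pathways. Neither mentions blocking or says whether the arms have separate lists.

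**Shams.** The marrow sham is a sedated skin puncture followed by a saline-based placebo (5.1.4, 5.1.9). The cord placebo is Dextran 40-based, and no sham harvest is described for it (5.2.7).

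**Covariates.** Section 9.1.2 names Age, intracranial volume for macrostructure, and a general provision to "evaluate the comparability of our groups on key demographic variables and will covary variables if necessary (e.g., socioeconomic status"). Arm is not named.

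**The concern.** The two definitions of the imaging groups classify the cord blood recipients differently. Under one they are treated; under the other they are comparators or absent. Imaging is the first efficacy measure in 1.2, section 2.2 calls a structural variable the primary measure of efficacy, and 6.4.9 expects these data to help power later studies. The group definition should therefore not be left to interpretation.

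The second issue is the model. Marrow and cord children are two separately recruited populations, allocated at different steps and given different shams. A model with Group alone leaves any difference between those populations in the error term, and leaves the estimate open to confounding if the treated-to-sham ratio differs between arms. What is at stake is the validity and precision of cells versus sham, not a comparison of the two products.

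**Working it through.** **Inputs.** 30 children, 15 per arm, 2:1 treatment to sham (section 3). The documents give no SD for any imaging or functional outcome, so every difference below is an assumption in SD units.

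**1. Counts.** 2 x 15 = 30, which reproduces the plan's total. Expected per arm: 15 x 2/3 = 10 treated and 15 x 1/3 = 5 sham; overall 20 and 10.

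**2. What the 6.4.2 label would mean if taken literally.**
- +BMMNC: 10 marrow recipients.
- -BMMNC: 5 marrow shams + 10 cord recipients + 5 cord shams = 20. Of these, 10/20 = 50% received cells and 15/20 = 75% come from the cord arm, against none in +BMMNC.
- If both products had the same effect d, the contrast would be d - (10d + 10 x 0)/20 = d/2.
- If the cord arm were instead left out, the comparison would be 10 versus 5.

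**3. Where an arm difference enters each planned model.** In the repeated-measures model the treatment effect is Group x Time, which is tested on within-child changes. If the cord arm is shifted by a constant A at every visit, a child's change is (y1 + A) - (y0 + A) = y1 - y0, so A drops out. With complete data and 10:5 per arm, a numerical check gave the same Group x Time F (10.708) for stable arm differences of 0, 1.0 and 1.5 SD. Only an arm difference in change remains in the error, and only an arm x Time term removes it. In the single-time brain-behavior models, an arm difference in level stays in the error and a plain arm term removes it.

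**4. Size of the precision cost.** Let D be the arm difference in the relevant quantity (change or level), in units of its within-arm SD. With equal arms, omitting the term raises the residual variance from 1 to about 1 + D^2/4. The ratio of standard errors, with the term to without it, is 1/sqrt(1 + D^2/4).

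| D | Ratio | Shorter with the term |
|---|---|---|
| 0.5 | 1/sqrt(1.0625) = 0.970 | 3% |
| 0.8 | 1/sqrt(1.16) = 0.928 | 7% |
| 1.0 | 1/sqrt(1.25) = 0.894 | 11% |

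Stated the other way, the standard error without the term is 3% to 12% larger (sqrt(1.0625) = 1.031; sqrt(1.25) = 1.118).

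A simulation of one outcome per child (5,000 runs, exactly 10:5 per arm) agrees. At D = 1 and no effect, the rejection rate is 0.029 without the term and 0.054 with it. The estimates vary equally (SD 0.39) and are unbiased either way, so the cost here is an overstated standard error and a conservative test.

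**5. Imbalance between arms.** The unadjusted Group estimate shifts by D x (cord share of treated - cord share of sham).
- 10:5 and 10:5: 10/20 - 5/10 = 0.
- 9:6 marrow and 11:4 cord: 11/20 - 4/10 = 0.15 D.
- 8:7 marrow and 12:3 cord: 12/20 - 3/10 = 0.30 D.

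Under simple 2:1 randomisation (an assumption), the treated counts in the two arms differ by 2 or more with probability 0.56. At D = 1 the simulated SD of the estimate is then about 0.44 without the term and 0.40 with it. At D = 0 the term costs a little: 0.41 without and 0.42 with, when there is no treatment effect.

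**The case against.** **The label.** Section 6.4.2 is a statement of purpose at the head of an acquisition section and specifies no test. Sections 1.2, 6.4.9 and 9.1.2 all compare treatment with control. A reader might infer that cord blood recipients will be analysed as controls, halving the effect and removing much of the power. The documents do not support that: it is the result of an analysis that the statistical section does not plan. This part of the objection stands, and what is left is a contradiction in wording.

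**The model.** A stable difference between arms cancels from Group x Time, so adding arm alone, at one degree of freedom, would do nothing for the main imaging test. This also stands. It is why the repair needs arm x Time, and why the 3% to 11% applies to an arm difference in change for those models and to a difference in level only for single-time models.

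**Bias.** A reader might infer that omitting arm biases the result. At exactly 10:5 in each arm it does not. Confounding needs an unequal split or unequal losses, together with arms that differ in the quantity tested.

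**Existing covariates.** The provision in 9.1.2 could be stretched to arm. It concerns demographic variables, applies only if judged necessary, and commits to nothing on arm, so it does not answer the point.

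**Importance.** Section 9.2 calls this primarily a safety study, and these outcomes are secondary. That limits the weight of the point but does not remove it.

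**Conclusion.** The point holds in two limited parts.

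First, 6.4.2 contradicts 1.2, 6.4.9 and 9.1.2 on who belongs to the comparison group, and about 10 of 30 children are affected. The intended reading is very probably treatment versus control.

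Second, the 9.1.2 models ignore the arm in which children are recruited and randomised. The cost is a standard error that adding the term would shorten by about 3% to 11%, if the arms differ by 0.5 to 1.0 SD in change (imaging) or in level (single-time models). There is no loss if they do not differ. If the split is uneven, the estimate also shifts by 0.15 to 0.30 of the arm difference in the examples shown. Losses could produce the same unevenness, since section 8.5 does not replace randomised children.

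These sizes rest on assumed arm differences, and the imbalance probability rests on simple randomisation, because the documents give neither an SD nor a blocking scheme. The primary safety objective is not affected.

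**What to change.** - **Section 6.4.2:** replace the +BMMNC / -BMMNC label with randomised cells (BMMNC or hUCB) versus sham, in agreement with 6.4.9 and 9.1.2.
- **Section 9.1.2, repeated-measures imaging models:** add arm (marrow, cord) and arm x Time as prespecified terms, and exempt them from the trimming of non-significant terms.
- **Section 9.1.2, single-time models in which group is a factor:** add arm as a fixed term.
- **Reporting:** show the cells-versus-sham estimate with its interval within each arm, as description only. With about 10 versus 5 children per arm, no test of a difference between arms should be read into it.

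**Cost.** A few sentences of text, with no change to trial conduct. Arm uses 2 - 1 = 1 degree of freedom. With three assessments, arm x Time uses (2 - 1) x (3 - 1) = 2 more. If the arms turn out not to differ, the loss of precision is slight.
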